Study Duration	Study duration is anticipated to be approximately 4 months
Study Center(s)	Approximately 3 sites in the United States
Objectives	The primary objective of this study is to establish the superiority of VerTouch versus the conventional palpation technique for the number of insertion attempts required in diagnostic and therapeutic neuraxial procedures.
Number of Subjects	It is expected that approximately 120 subjects will be screened to meet a target enrollment goal of 96 subjects.
Main Inclusion / Exclusion Criteria	Inclusion Criteria 
1. Males and females aged 18 years and above, inclusive2. Subjects scheduled for one of the following procedures:
• Diagnostic LP (collection of CSF and/or measurement of ICP to diagnose hemorrhaging or neurological infections)• Therapeutic LP (intrathecal injection of therapeutic agents; drainage of CSF to treat pseudotumor cerebri)• Planned orthopedic or obstetric procedure, such as labor/induction, cesarean section,

hysterectomy, or total hip/knee replacement, with neuraxial anesthesia (injection of anesthetic into spinal and/or epidural space to reduce pain during procedure)

- Epidural blood patch (use of autologous blood to close holes in the dura mater and relieve PDPH)
- 3. Subjects having a BMI $\leq 42\text{kg}/\text{m}^2$

Exclusion Criteria

1. Patient does not provide informed consent
2. Skin or soft tissue infection near the puncture site
3. Allergy to local anesthetic
4. Uncorrected coagulopathy
5. Acute spinal cord trauma
6. History of lumbar spinal surgery
7. Prior known failed neuraxial anesthesia
8. Diagnosed scoliosis, thoracic kyphosis, lumbar lordosis, scleroderma, or ankylosing spondylitis, or lumbar spinal stenosis
9. Incarcerated subjects

Study Device	VerTouch™
Duration of Device Exposure	< 2 hours
Reference Therapy	Conventional palpation technique used for spinal needle placement
Endpoints	
Primary Endpoint:
 
The number of insertion attempts (any forward movement of the needle following puncture of the skin) in the study device group as compared to the control group (palpation). Attempts are counted until confirmation of spinal canal access can be assessed.
 
Secondary Endpoints:
 
 1. Incidence of first-insertion success (a case that does not require any reinsertions, but can include any number of redirections) 2. Number of redirections (any forward movement of the

needle in a new direction not preceded by withdrawal from the skin, counted until confirmation of spinal canal access can be assessed)

3. Number of passes (any forward movement of the needle, calculated as the sum of insertions and redirections)
4. Incidence of first-pass success (a case that does not require reinsertions or redirections)
5. Subject discomfort during landmarking on a 100mm VAS scale
6. Provider confidence with the identified insertion site on a 1-5 Likert scale
7. Procedure success as confirmed by the following procedure-specific methods:
 - Epidural anesthesia: able to achieve a T10 or greater bilateral sensory level change to cold
 - Spinal anesthesia: able to achieve sensory blockade to surgical stimulus at level desired
 - Diagnostic and therapeutic LP: return of CSF
 - Blood patch: able to inject homologous blood into epidural space (entry confirmed by loss-of-resistance)

Tertiary Endpoints:

1. Localization time (time from first touch of draped patient to identification of an insertion site; for VerTouch, this is the time from device placement to movement of the applicator to the identified insertion site)
2. Insertion time (time from retrieval of marker or local anesthetic assembly until no further needle advancements are made)
3. Number of bone contacts
4. Incidence of referral to radiology

Safety Endpoints

1. Incidence of post-dural puncture headache (PDPH)
2. Incidence of unintended dural puncture (specific to epidural anesthesia)
3. Incidence of paresthesia during needle insertion (specific to neuraxial anesthesia)
4. Incidence of traumatic tap (results in visible blood)

aspiration)

Exploratory Endpoints:

1. Procedure time (from positioning of the patient to removal of the drape from the subject's back)
2. Incidence of conversion from spinal to epidural (specific to neuraxial anesthesia)

Statistical Methods

The primary endpoint will be analyzed using a bootstrap approach for the null hypothesis that VerTouch requires more insertions than palpation. A one-sided 0.025 p-value will be considered as the cut-off for statistical significance.

Abbreviations

2D	2-Dimensional
AE	Adverse Event
BMI	Body Mass Index
CI	Confidence Interval
CFR	Code of Federal Regulations
CRNA	Certified Registered Nurse Anesthetist
CV	Curriculum Vitae
eCRF	Case Report Form
EM	Emergency Medicine
ESI	Epidural Steroid Injection
FDA	Food and Drug Administration
GCP	Good Clinical Practice
HIPAA	Health Insurance Portability and Accountability Act of 1996
ICH	International Conference on Harmonization
IFU	Instructions for Use
IRB	Institutional Review Board
ITT	Intent to Treat
LA	Local Anesthetic
LP	Lumbar Puncture
NP	Nurse Practitioner
NSR	Non-Significant Risk
OTC	Over the Counter
PA	Physician's Assistant
PDPH	Post-Dural Puncture Headache
PM	Pain Medicine
PHI	Protected Health Information
PP	Per Protocol
SAE	Serious Adverse Event
SAP	Statistical Analysis Plan
SD	Standard Deviation
UADE	Unanticipated Adverse Device Effect
US	United States
VAS	Visual Analog Scale

1 Study Contact Information

2.1 Background

Neuraxial procedures, in which a needle is inserted into the spinal canal through a gap in the vertebrae, are performed at a rate of nearly 13 million per year in the US, across a myriad of diagnostic and therapeutic clinical scenarios. Among these are the 800,000 lumbar punctures (LPs) conducted to diagnose subarachnoid

hemorrhage or neurological infection, or to treat neurological diseases^[1]. There are also 3.1 million deliveries of neuraxial anesthesia to reduce pain during obstetric and orthopedic procedures, such as labor/induction, hysterectomy, and total hip/knee replacement^[2,3]. Additionally, there are 9 million epidural steroid injections (ESIs) for back and leg pain relief^[4]. Finally, there are epidural blood patch procedures, in which autologous blood is used to close holes in the dura mater and relieve post-dural puncture headache (PDPH).

The standard of care involves manual palpation of the patient's back to detect the spinous processes (SPs) and estimate the location of the interspinous needle insertion site^[5,6]. While providers are trained to perform these procedures with meticulous precision and attention to detail, this technique remains highly inaccurate, often requiring multiple insertion attempts to properly place the needle^[7,8]. These attempts lead to patient pain and complications, such as traumatic taps and PDPHs; unpredictable procedure times; and poor facility throughput^[9,10]. The challenge is only exacerbated in patients with high body mass index (BMI), a factor that already accounts for 13.8% of procedure failures, and is only worsening in the US^[11,12].

Challenging cases are often referred to radiology for fluoroscopic guidance, at rates greater than 47% in settings such as emergency medicine (EM)^[13]. However, fluoroscopy exposes patients and providers to unnecessary radiation, can rarely be used in perioperative settings, and is associated with high costs for overhead, patient transport, and assembly of a radiology team^[14-16]. Ultrasound may also be used to help visualize the vertebrae in challenging cases^[17]. However, the modality requires significant training on how to interpret its output, and is cumbersome, requiring a gel medium and manipulation of a needle in combination with an unstable probe.

VerTouch™ is a novel device that holds promise to reduce the ambiguity associated with the palpation technique, and to overcome the shortcomings of other imaging-based solutions. VerTouch employs scanning-based tactile imaging to detect spinal landmarks, analogous to those sensed during palpation^[18]. When pressed against the subject's lower back, the Device's imaging component detects the differences in hardness surrounding the spinous processes. In real-time, data collected by the device are processed and visualized as the TactoMap™, a 2D pressure map on a full-color display, from which the operator can accurately and intuitively identify a suitable insertion site. VerTouch can be used to mark the identified site with a supplied surgical marker, or to inject local anesthetic and place an introducer or spinal needle to a safe depth at that site. The Device is then removed, and the procedure is completed in the standard manner.

VerTouch has the potential to require minimal training, cause no additional discomfort to the patient, and be seamlessly integrated into any neuraxial procedure. By providing the information needed to reveal the underlying lumbar anatomy, VerTouch has the potential to help the provider identify an accurate insertion site, and have a greater likelihood of success on the first insertion attempt. With the potential to reduce the number of needed insertions, VerTouch may reduce the frustration, pain, and complications associated with these procedures, and standardize the time associated with both the localization and insertion steps. Combined, these potential benefits may translate into lower associated costs of care for factors like bed and boarding time, as well as readmissions and/or further treatment^[19-21].

2.2 Rationale

This study is intended to evaluate the use of VerTouch to reduce the number of insertion attempts compared to the conventional manual palpation technique.

3 Device Description

VerTouch is a handheld device, which is capable of assembly and use by a single operator, and requires no connection with peripheral systems or software during clinical use^[22,23]. VerTouch includes reusable and disposable parts (**Figure 1**).

[figure not shown]

Figure 1. Exploded, oblique view of VerTouch subsystems, including the disposable Base and Sleeve, and reusable Monitor. In this figure, 'needle guide' broadly references all needle and marker guidance elements, including the Restrictor.

Not shown are the reusable Charging Station, Power Adapter, and PC Connector, none of which are directly used for clinical operation; as well as the Disposable Packaging, which includes a dedicated mini surgical Marker, and a Dock to facilitate sterile assembly of VerTouch components.

The reusable Monitor is the subsystem that performs image acquisition, processing, and display of the TactoMap. It comprises a rechargeable battery, and is sold with a charging station to support repeated use. The disposables include a device Base and a Sleeve, both of which are single use, and provided terminally sterilized via ethylene oxide (EtO). The Base allows for placement of the device against the back, and includes the interactive components for scanning-based imaging and needle or marker guidance; while the Sleeve prevents contamination from the Monitor during use. Further description on these components can be found below; please see the Instructions for Use (IFU)^[24] for more detail and illustrations.

3.1 Assembly

The sterile disposable components, including the Base, the Sleeve, and a dedicated surgical Marker are supplied in a two-part tray. The Tray is wrapped in a Drape, which is used to create a sterile field for the device. The wrapped Tray comes in a sealed Pouch, along with a disposable Dock, which is used to permit sterile electromechanical assembly between the disposable Base and reusable Monitor. The Device powers on upon assembly, after which the sleeve can be slid over the Monitor, forming the protective barrier.

3.2 Workflow Selection

VerTouch can be used to support needle insertion via any of three workflows: marking, placement of a 20-22G, 3.5" or 5" needle, or placement of an introducer. With the marking workflow, the device is used to mark an identified insertion site, but local anesthetic (LA) injection and needle insertion occur after device removal. With the introducer and needle placement workflows, LA is injected, and the needle or introducer is placed to a safe depth, through a depth-limiting mechanism (Restrictor) integrated into the device (**Figure 2**; see Section 9.2.1 for further description).

The remainder of the insertion is then completed after Device removal, which is enabled by a Needle Release Gate (Gate). Prior to beginning the procedure, the user selects their target workflow. If pursuing a marking workflow, the Needle Guide can be removed by pulling up the Removal Tab, which reveals the larger-diameter Marker Guide, and replaced later, if needed.

[figure not shown]

Figure 2. Oblique view of Needle Guide, with Restrictor in 5"-needle position.

3.3 Device Placement

With VerTouch, users continue to use standard landmarking techniques to identify a safe level for the procedure area. This is typically done by palpating for the tips of the iliac crest, which approximately align with the L4-5 interspinous space. This is performed prior to draping the patient, such that the procedure area is exposed and used to guide Device placement. After Device assembly, the user then grips the Handle on the Base with his/her left hand, and places the assembled Device against the patient's back. Midline indicators on the Device can be used to support alignment with the midline of the spine. A rubber Bottom Pad on the Base prevents slippage of the Device along the back during use.

3.4 Imaging

The Applicator is the primary component that facilitates scanning-based tactile imaging. A calibrated, piezoresistive sensor array (Sensor) is mounted to the patient-contacting surface of the Applicator, which is designed to optimize feature resolution with minimal application of force (**Figure 3**).

[figure not shown]

Figure 3. Bottom view of assembled VerTouch, highlighting sensor mounting.

The Applicator is assembled with a Carriage mechanism that is mounted to a fixed Track the length of at least two SPs in the indicated patients. Via an Applicator Button accessible by the user's right hand, the Applicator can be slid along the craniocaudal (y) axis via the Track; and can be pressed along the anteroposterior axis (z), via a spring mechanism that facilitates 2 cm of tissue penetration. A flexible printed circuit board assembly (PCBA) connects the Sensor to downstream electronics and allows for free y- and z-axis movement; an elastomeric (y-lock) strip ensures that the Applicator cannot slide while being pressed. When the user presses the Applicator at a first location, a linear positioning system is used to display the corresponding 2D pressure data at that location within the imaging range on the screen. The user then slides the Applicator to a new location, and repeats the process until the imaging range is complete. A Force Gauge on the screen (not included in **Figure 3**) indicates the approximate force of each press to help the user apply the same force across presses. Throughout the imaging process, the user observes the outputted pressure data with the goal of identifying a blue region along the midline corresponding to an interspinous space. Navigation Buttons on the left side of the Monitor (not visible in **Figure 3**) can be used to adjust screen brightness and/or scanning sensitivity during imaging. In the event of any misalignment and/or the lack of an interspinous space, the image can be reset via an operator-facing Reset Button on the Monitor, and scanning can be performed at a new location.

3.5 Insertion

The Needle Guide is reversibly attached to the top (cranial side) of the Applicator, and its location is presented as a crosshair overlay in the imaging screen. Once an insertion site is identified, the user slides the Applicator until the crosshair aligns with that site. If a marking workflow has been selected, the user places the Marker directly through the exposed Marker Guide. He/she then removes the Device, and injects LA and inserts his/her preferred needle on the mark. For the placement workflows, LA is first injected directly through the Needle Guide. For introducer placement, the user then places the introducer through the Needle Guide. The Gate is then opened, which allows the Device to be removed from the partially placed introducer. Following Device removal, the introducer is fully inserted and the preferred spinal needle is placed through it. The same is done for needle placement; however, to ensure the needle does not exceed a safe depth while the device is in place, the earlier-described Restrictor is used. The Restrictor is pushed over to align with the Needle Guide for placement of a 3.5" needle; and it is further pulled up for placement of a 5" needle (**Figure 4**). Locking mechanisms ensure the Restrictor locks in both positions.

[figure not shown]

Figure 4. Side view (cranial) of VerTouch Needle Guide, depicting Restrictor configurations for safe placement of an introducer, and 3.5" and 5" needle, extracted from the IFU^[24].

After needle placement, the Gate is opened to allow the device to be pulled away from the introducer or needle. This is accomplished by sliding the Device downward, craniocaudally; and then leftward, mediolaterally (as viewed against the patient's back).

With any workflow, the ability of the system to assist with accurate insertion-site identification has the potential to be associated with a reduction in insertion attempts, although some redirections may still be necessary considering the fixed, perpendicular orientation of the Needle Guide. All Needle and Marker Guide interactions are performed with the right hand, per standard needle insertion training, regardless of handedness.

3.6 Disassembly

Upon needle access to the spinal canal, the user completes his/her procedure per standard protocol. Following the procedure, the Sleeve and Monitor are disconnected from the Base. The Monitor is dropped into the dock, while the remaining components are disposed of with other disposable procedure components.

3.7 Monitor Maintenance

After each use, the Monitor is cleaned for visible contaminants. It is then brought to a storage location and placed on the VerTouch Charging Station. The Power Adapter is used to connect the Charging Station to an outlet for Monitor recharging. Note that the Device cannot be used while charging, as the Base and Charging Station connect to the same connection port on the Monitor.

For study use, the Charging Station also has a data transfer port that allows for connection to a PC for transfer of study data that can be referenced when

investigating anomalous findings and/or can be used to establish a database of human TactoMaps for future development. For a given subject, firmware in the Monitor captures pressure data corresponding to the final scan that was used to identify an insertion site. Sampled at a rate of at least 10Hz, these include Sensor readings before and after integration into the full scanning range (referred to as push images and built images, respectively). Also included is header information for each sample, including the current timestamp, sensitivity value, linear position value, and force level. To provide additional information, users can flag the frame at which the Applicator was moved to align the Needle Guide with their identified site by pressing and holding the central Navigation Button on the Monitor. Data transfer software is loaded onto on-site study PCs, which allows for upload of these data from the Monitor following each procedure.

3.8 Maintenance Mode

VerTouch also has a touchscreen-enabled maintenance mode, which can be operated by a non-clinical user to adjust time and date settings, and/or to perform password-protected firmware updates.

3.9 User and Subject Characteristics

Patients undergoing neuraxial procedures have varying characteristics, though most receiving neuraxial anesthesia for obstetric procedures are pregnant. Indicated patients have a BMI of $\leq 42\text{kg/m}^2$ and may be in the seated or lateral decubitus position.

The Device is intended for use by all providers credentialed to perform these procedures. **Table 1** summarizes some such providers, as well as procedure-specific information, such as the VerTouch workflow(s) applicable to each procedure.

Table 1. Intended Users and Procedures

Name	Applicable Workflow(s)	Settings	Locations	Providers
Diagnostic LP	Needle placement, marking	EM	Emergency Room	EM Physician, PA
		NE	Neurology Suite	Neurologist, Neurosurgeon, PA
Therapeutic LP	Needle placement, marking	NE	Neurology Suite	Neurologist, Neurosurgeon, PA
Neuraxial Anesthesia	Marking, introducer placement	AN	Operating Room	Anesthesiologist, CRNA
Blood Patch	Marking	AN	Operating Room	Anesthesiologist, CRNA
ESI	Marking	PM	PM Suite	PM Physician, PA, CRNA
		AN	Operating Room	Anesthesiologist, PA, CRNA
PA = physician assistant; CRNA = certified registered nurse anesthetist; NE = neurology, AN = anesthesiology (includes obstetric and orthopedic); PM = pain medicine				

Note that users may have either handedness, and be seated or standing during use. MDs may include residents (a type of clinical trainee), fellows, and attendings. Not listed below are nurse practitioners (NPs), who are credentialed to perform neuraxial procedures in some facilities. In some states, anesthesiology assistants (AAs) may also perform these procedures in the anesthesiology setting.

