- BMI (kg/m^2): underweight (<18.5), normal (18.5-24.9), overweight (25-29.9), class 1 obesity (30.0-34.9), class 2-3 obesity (≥ 35.0)
- Age (years): adolescent (<22), young adult (22-40), middle-aged adult (41-65), older adult (>65)
- Provider type: MD, PA, CRNA, AA, NP
- Provider specialty: emergency medicine, neurology, anesthesiology
- MD level (MDs only): resident, fellow, attending
- Provider years in practice: <5 , 5-10, >10
- Provider experience (number of neuraxial procedures in past 12 months): 5-25, 26-50, 51-100, >100

- Neuraxial procedure: diagnostic LP, therapeutic LP, neuraxial anesthesia, blood patch
- Medication given for procedure: none, pain, anti-anxiety
- Needle type: spinal 20-22G cutting, spinal 20-22G non-cutting, spinal >22G, Tuohy, CSE
- VerTouch workflow (VerTouch subjects only): marking, introducer placement, needle placement

Subgroup levels will only be considered if there are at least 8 subjects within the covariate level across both treatments.

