8.1 General Reporting Conventions

Summary tables will be generated to support the analysis using the subject treatment as a group. The numeric descriptive statistics include the n (observed data), mean, standard deviation (SD), median, minimum value, and maximum value. Categorical summaries will show the number and percent of subjects in the levels associated with the variable summarized and the analysis performed. Percentages will be calculated based on the total number of subjects with non-missing data for the assessment. The denominator should be included on each table to indicate the set of subjects included in each analysis.

Statistical Analysis Plan

Client/Project	IntuiTap/VerTouch
Version and Date	V02 – 22 December 2020

Statistical analyses will be performed to assess the homogeneity of the study populations, evaluate the primary hypothesis, and evaluate the impact of covariates on the performance of the VerTouch device. Standard statistical tests used for hypothesis testing are the t-test for numeric measures and the likelihood ratio chi-square test for categorical variables. For categorical variables with small cell counts (less than 5), Fisher's exact test will be used. For inferential analyses, unless otherwise indicated, a two-sided p-value of less than or equal to 0.05 will be considered statistically significant. All confidence intervals (CIs) will be two-sided 95% intervals. Note that p-values reported for tertiary and exploratory endpoints will be used for reporting purposes but are not to be considered for use in product labeling.

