8.3.3.4 Covariate and Other Supporting Analyses

The ANOVA model based on the log(attempts) will consider each of the following covariates one at a time with the factor, treatment, and factor-treatment interaction. The n, mean, and standard deviation (SD) of values for the number of attempts by factor levels will be provided by treatment group. Subgroup levels will only be considered if there are at least 8 subjects within the covariate level across both treatments. The covariates to be analyzed are:

- BMI (kg/m²): underweight (<18.5), normal (18.5-24.9), overweight (25-29.9), class 1 obesity (30.0-34.9), class 2-3 obesity (≥ 35 .0)
- Age (year): adolescent (<22), young adult (22-40), middle-aged adult (41-65), older adult (>65)
- Provider type: MD, PA, CRNA, AA, NP
- Provider specialty: emergency medicine, neurology, anesthesiology
- MD level (MDs only): resident, fellow, attending
- Provider years in practice: <5, 5-10, >10
- Provider experience (number of neuraxial procedures in past 12 months): 5-25, 26-50, 51-100, >100
- Neuraxial procedure: diagnostic LP, therapeutic LP, neuraxial anesthesia, blood patch
- Medication given for procedure: none, pain, anti-anxiety
- Needle type: spinal 20-22G cutting, spinal 20-22G non-cutting, spinal >22G, Tuohy, CSE
- VerTouch workflow (VerTouch subjects only): marking, introducer placement, needle placement

Statistical Analysis Plan

Client/Project	IntuiTap/VerTouch
Version and Date	V02 – 22 December 2020

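### VerTouch workflow and provider type are partly nested in setting, and the one-at-a-time covariate models omit setting, so a setting difference can appear as a workflow or provider effect

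*Protocol*

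**What the plan says.** Protocol 3.9 states that Table 1 "summarizes some such providers, as well as procedure-specific information, such as the VerTouch workflow(s) applicable to each procedure". The table pairs procedures with workflows, settings and providers. The two LP rows, in EM and neurology, allow "Needle placement, marking". The neuraxial anesthesia row allows "Marking, introducer placement". Blood patch, also in anesthesiology, allows marking only. PAs appear in the LP rows and CRNAs in the anesthesia and blood patch rows. The only row placing PAs in anesthesiology is epidural steroid injection, which is not an eligible procedure (Protocol 6.4.5). Physicians and the marking workflow occur in all three settings.

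Under Protocol 3.2 the user chooses the workflow, so it is not randomized. Protocol 7.3 randomizes 1:1 in blocks within setting.

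SAP 8.3.3.4 says its ANOVA on log attempts "will consider each of the following covariates one at a time with the factor, treatment, and factor-treatment interaction". The list includes "Provider type: MD, PA, CRNA, AA, NP" and "VerTouch workflow (VerTouch subjects only): marking, introducer placement, needle placement". Provider specialty and neuraxial procedure are on the same list, each in its own model. A level is considered only if it has at least 8 subjects across both arms. SAP 8.1 gives one purpose of the analyses as to "evaluate the impact of covariates on the performance of the VerTouch device". Protocol 8.2.2 labels the covariate analyses exploratory.

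**The concern.** When a factor's levels occur in different settings and the model has no setting term, the factor's estimate absorbs whatever differs between settings. Introducer against needle placement is, by Table 1, wholly anesthesia against LP. A CRNA level is, by the same table, drawn wholly from anesthesiology.

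The two factors are exposed in different ways. Workflow is analysed in VerTouch subjects only, so there is no palpation arm to cancel a setting that is simply harder. Provider type is fitted with treatment, and the term that bears on device performance is provider-by-treatment. Because arms are balanced within setting, that term is distorted when the device effect itself differs by setting.

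At stake is what the trial says about who uses the device well and which workflow works best. The sponsor already makes statements on provider skill and workflow equivalence from formative and bench testing (Protocol 9.2.1 and 9.2.1.1), and these results would be read against them. The same confounding can also hide a real difference.

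**Working it through.** **The plan's own figure.** The documents give no operating characteristic for the covariate models. The nearest checkable figure is 90% power for first-attempt success, 50% against 81%, 48 per group, two-sided 0.05. With a pooled rate of 0.655:

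z = (0.31 × √48 − 1.96 × √(2 × 0.655 × 0.345)) / √(0.50 × 0.50 + 0.81 × 0.19) = (2.148 − 1.318) / 0.636 = 1.31, so power is 90.4%.

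The figure reproduces, and the present point does not depend on it.

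**Inputs from the documents.** 96 subjects, 1:1 within setting; settings approximately even (32 each taken); log(attempts); alpha 0.05. PAs and needle placement occur only in EM and neurology, CRNAs and introducer only in anesthesiology, MDs and marking everywhere.

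**Assumptions.** Attempts are 1 plus a negative binomial count (size 0.8). Non-MD share and non-marking share are 20% and 30%, 50% and 50%, or 80% and 80%. There is no true provider or workflow effect. Setting means lie within 1.1 to 3.3. There are 2,000 trials per cell, so the Monte Carlo standard error at 5% is √(0.05 × 0.95 / 2000) = 0.5 points.

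**Tests.** Provider-by-treatment: F test of adding provider × treatment to provider + treatment, then the same with setting and setting × treatment in both models. Workflow, VerTouch arm only: F test of workflow against the mean, then with setting in both models.

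Rejection rates (%) for the three share levels; means are EM/neurology/anesthesiology:

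| Palpation; VerTouch means | Provider × treatment, planned | With setting terms | Workflow, planned | With setting |
|---|---|---|---|---|
| 2.1 all; 1.3 all | 3.8, 4.9, 5.2 | 4.4, 5.0, 4.4 | 4.8, 4.4, 4.7 | 5.1, 4.9, 5.1 |
| 2.6/2.1/1.6; 1.6/1.35/1.1 | 4.7, 4.2, 3.8 | 4.8, 4.2, 3.8 | 7.7, 9.7, 17.5 | 3.8, 3.2, 3.8 |
| 2.6/2.6/1.3; 1.7/1.7/1.1 | 3.2, 3.7, 6.8 | 4.6, 3.5, 4.9 | 11.3, 18.9, 37.0 | 3.8, 4.3, 4.2 |
| 2.1/2.1/1.4; 1.8/1.8/1.1 | 4.3, 2.9, 3.7 | 5.1, 3.6, 5.1 | 9.5, 22.1, 46.9 | 4.2, 3.4, 4.1 |
| 2.1 all; 1.1/1.1/2.1 | 10.8, 24.9, 36.8 | 5.9, 8.4, 6.8 | 31.6, 56.9, 80.5 | 12.3, 13.1, 12.5 |
| 3.3/3.3/1.3; 1.1/1.1/1.3 | 16.2, 55.7, 85.4 | 5.0, 5.0, 4.1 | 11.4, 14.2, 18.8 | 7.2, 7.7, 8.0 |

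In rows 2 to 4 the settings differ in difficulty in both arms. In rows 5 and 6 the device effect differs by setting.

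**Second count model, nearer the plan's means.** Geometric counts, VerTouch 1.15 everywhere, palpation 2.3 in EM and neurology, 40% PAs there. Provider-by-treatment rejected as follows:
- CRNAs at 20% of anesthesiology cases: 10.6% (anesthesiology palpation mean 1.3) and 9.2% (1.5).
- CRNAs at 50%: 20.9% (1.3), 13.2% (1.5) and 7.1% (1.8).
- CRNAs at 80%: 37.1% (1.3).

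Where it was refitted with setting terms (1.3 and 1.5 at 50%, 1.3 at 80%), the rate was 4.3% to 4.4%.

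For workflow, with 70% of cases using placement rather than marking, VerTouch means of 1.3 for LP and 1.05 for anesthesia gave 10.3% pooled and 3.6% within procedure. Means of 1.5 and 1.1 gave 18.2% and 4.1%.

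**The case against.** A reader might infer that any setting difference will be reported as a provider or workflow effect. The documents do not support that. A real setting difference is needed, and in most of the scenarios above the test still fails to reject in the majority of trials.

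A reader might also infer that harder settings alone corrupt the provider result. With randomization within setting they largely do not: provider-by-treatment stayed at 3% to 7% when both arms were harder together. The provider main effect is confounded (18% to 86% in row 3), but it is not an effect on device performance. One qualification applies. If palpation averages 2.6 in EM and neurology and 1.3 in anesthesiology, a constant ratio needs VerTouch to average at least 2.6 / 1.3 × 1.0 = 2.0 in EM and neurology, since a count cannot fall below 1. That is a pooled mean of at least (2.0 + 2.0 + 1.0) / 3 = 1.67, against the 1.1 the plan assumes. Near that floor, a difficulty gradient under palpation tends to become a difference in device effect.

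Other points stand:
- Table 1 describes intended users, and only some of them; it is not the investigator roster. NPs are unlisted, and AAs appear only in the text. The tie is complete only for introducer against needle placement.
- Specialty and procedure are tested too, so a setting pattern would be visible. Separate models still do not separate it from provider or workflow.
- No document gives provider or workflow shares, and the highest rates need extreme shares and means together.
- The analyses are exploratory, and no decision is attached to them.

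**Conclusion.** The concern holds as a limited one. Workflow and provider type are partly nested in setting, and the planned models cannot separate them from it. It is strongest for workflow, where a difference in difficulty between settings suffices: 8% to 47% rejection in place of 5% with no true workflow effect, and 3% to 4% once setting is added. If VerTouch attempts do not vary by setting, the workflow test keeps its nominal level. For provider type the problem arises if the device effect differs by setting: 11% to 85% across the negative binomial scenarios and 7% to 37% with means nearer the plan's, falling to 4% to 8% wherever setting and setting-by-treatment were added.

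The size rests on assumed shares, setting means and count distributions; the direction rests only on Table 1 and SAP 8.3.3.4. A reader should not extend this to the primary test or the secondary sequence, which do not use these models. Nor should it be extended to BMI, age or the other listed factors, for which Table 1 shows no such nesting and no check was made.

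**What to change.** In SAP 8.3.3.4, and to match in Protocol 8.2.2:

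1. Add setting to the workflow model. Setting-by-treatment cannot be fitted there, because only one arm is analysed.
2. Add setting and setting-by-treatment to the provider-type model.
3. Report n, mean and SD for these two factors within setting.
4. State that introducer and needle placement are not compared with each other, because they share no procedure. An adjusted model would still yield an indirect contrast through marking, valid only if marking's relation to the other workflows is the same in both procedures.

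The cost is wording and a few model terms; setting is already the randomization stratum and is recorded. The downside is fewer degrees of freedom, low power and some cells too small to report. With 48 / 3 = 16 VerTouch subjects per setting, an assumed 5 against 11 split of marking and introducer would detect 1.1 against 1.5 mean attempts only about 5% of the time. Adjustment is also not a full cure: when the device effect differed by setting, the adjusted workflow test still rejected in 7% to 13% of trials because variances were unequal, so the within-setting summaries should carry the interpretation.
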